9.11 Treatment Compliance

Treatment compliance will be confirmed by maintenance and close reviews of the drug accountability records.

9.12 Concomitant and Prohibited Therapies

9.12.1 Concomitant Therapies

All concomitant medications used (including over-the-counter medications and herbal supplements) will be recorded in the source document and in the eCRF. Furthermore, each change in concomitant medication (e.g., new treatment, discontinuation of treatment, change in dosage/route, etc.) during the study should be documented in the same way. Previous medication taken within the last 6 months prior to screening has to be recorded as well.

If patients received any previous treatment which is part of an exclusion criterion (for details, please refer to Section 8.2.2) they will not be eligible for study participation. Patients on ongoing treatment with phenytoin will be closely monitored (blood plasma level) due to the drug-drug interaction with cisplatin and 5-FU.

9.12.2 Prohibited Therapies

The following co-medication/therapies are not allowed during participation in the study:

- EGFR targeting agents apart from randomly assigned study medication until end of treatment.
- Any other immunotherapy until end of treatment.
- Any anti-cancer treatment other than described in this protocol until end of treatment.
- Ongoing regular doses of hydrocortisone and steroids (except for topical/inhaled) other than corticosteroids used for precaution of IRR.
- Immunosuppressive agents until end of treatment.
- Radiation therapy (except palliation of existing bone metastasis pain).
- Erythropoietin (Epo).
- Other medications that are contraindications to 5-FU and cisplatin or carboplatin respectively as per SmPC 4.3 “Contraindications” and 4.5 “Interaction with other medicinal products and other forms of interaction” (see Appendices F, G, H).

9.13 Treatment After End of Study

After the end of the study, i.e., in case of progression of disease or if other withdrawal criteria are met, patients will be treated by their physician according to most appropriate and best supportive standard of care.

10 STUDY PROCEDURES

Patients will provide written informed consent before any study-related procedures are initiated, including the cessation of prohibited concomitant therapy.

For an overview on the timing of assessments and procedures throughout the study, refer to the schedule of events (Section 18.1). Throughout the study, every reasonable effort should be made by study personnel to follow the timing of assessments and procedures in the schedule of events for each patient.

10.1 Study Periods and Schedule of Visits

10.1.1 Screening Visit

The patient must be screened within 28 days prior the day of first infusion.

The following records and assessments will be performed at screening:

- Obtain written informed consent.
- Contact the IWRS to obtain patient identification number.
- Check of inclusion/exclusion criteria.
- Check availability of pre-existing tumor tissue sample for EGFR and p16 status assessment.
- Demographic information (including age, race, smoking status and alcohol consumption).
- Diagnosis of SCCHN, including oncological information, previous chemotherapy and radiotherapy and other oncological regimens.
- Medical history apart from SCCHN, including current therapies (e.g., prescription and non-prescription medication).
- Record ECOG performance status.
- Physical examination including underlying disease, weight, height and BMI.
- Vital signs (blood pressure, heart rate and body temperature).
- 12-lead ECG.
- Echocardiogram (ECHO)/Multiple Gated Acquisition (MUGA) scan for confirmation of eligibility (exclusion criterion 13).
- Evaluation of tumor size by computed tomography (CT) or magnetic resonance imaging (MRI) (head and neck region, chest, and abdomen).
- Blood and urine sampling for safety laboratory (hematology, coagulation panel, blood chemistry and urinalysis). Please note that creatinine clearance needs to be assessed at screening unless previous results not older than 6 weeks are available.

- Blood sampling for genotyping (FcγRIIIa status; only in case the patient will enter the study, the blood sample might also be used at a later time point for further analyses like FcγRII status).
- Recording of previous and concomitant medication.

10.1.2 Randomization

If the patient is eligible to participate in this study (i.e., if all inclusion criteria are met and no exclusion criteria apply), the investigator will contact the IWRS for randomization information within 1 to 3 days prior to the next scheduled visit of the corresponding patient. The patient will be randomly assigned to receive either CetuGEX™ or cetuximab by receiving a unique randomization number (as detailed in Section 9.5). The patients do not need to visit the study site for this procedure but can be informed by phone.

Additionally, the pre-existing tissue sample will be sent to the central laboratory for the following analyses:

- EGFR expression by immunohistochemistry at a central laboratory. Further immunohistochemical assessments may be performed on the tumor sample if deemed necessary by the sponsor, e.g. tissue micro arrays to further characterize the tumor.
- p16 tumor suppressor gene status, indicative for high risk of Human Papilloma Virus (HPV) in the tumor (remaining tissue needs to be stored for further analysis in case of eligibility).
- Assessment of HPV status at a central laboratory.

These analyses may be performed at a later time point during the study.

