9.6 Blinding and Unblinding Treatment Assignment

Blinding at the level of study treatment does not apply since the study will be open label.

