c) If the administration of CetuGEX™ or cetuximab is skipped for any reason (see Sections 9.9.1 and 9.9.2), e.g., on Day 8, all assessments scheduled for this study visit day are to be performed as planned (i.e., including collection of blood samples for the determination of ADA and PK).

d) The platinum-based chemotherapy should be given within 24 hours after the infusion of CetuGEX™/cetuximab. Administration of 5-FU should be started within 24 hours after the infusion of CetuGEX™/cetuximab.

D = day, W = week

Day 0, Cycle 1 (Week 1)

On Day 0 of Cycle 1, eligible patients randomized to receive CetuGEX™ will visit the study site to receive their unique randomization number and perform baseline assessments as listed below and to receive a priming dose of 60 mg on this visit, after all baseline/safety assessments have been performed. The Day 0 visit is not applicable for patients randomized to receive cetuximab. General baseline assessments scheduled for Day 0 will be performed on Day 1 for those patients randomized to cetuximab.

The following assessments will be performed on Day 0 for patients in the CetuGEX™ treatment arm:

- Confirmation of inclusion/exclusion criteria.
- Physical examination.
- Vital signs (blood pressure, heart rate and body temperature), body weight and BMI.
- 12-lead ECG, if not done within 7 days prior start of study medication administration during screening phase.
- Record ECOG performance status.
- Blood and urine sampling for safety laboratory (hematology, coagulation panel, blood chemistry and urinalysis).
- Pregnancy test for female patients of childbearing potential.
- Quality of life questionnaires EORTC-QLQ-C30 and EORTC-QLQ-H&N35 (to be performed prior to any other assessments).
- Recording of concomitant medication.
- Assessment of AEs.
- Blood sampling for ADA testing.
- Blood sampling for PK assessments prior to the start of infusion and after the end of infusion.
- Blood sampling for assessment of cytokines and other relevant blood proteins (to be performed pre-dose, one hour after start of infusion and at the end of infusion).
- Blood sampling for assessment of immune status (to be performed pre-dose).
- Infusion of 60 mg CetuGEX™ priming dose.

Day 1, Cycle 1 (Week 1)

Day 1 of Cycle 1 will be the first treatment day for patients randomized to receive cetuximab. For those patients randomized to receive CetuGEX™ Day 1 of Cycle 1 should be performed within 24 hours after Day 0.

Day 1 (of each treatment cycle)

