10.3.2 Quality of Life Measures

To assess the QoL of each patient, patient-reported disease-related symptoms and health related QoL will be measured using the EORTC-QLQ-C30 questionnaire and the head and neck module (H&N35; according to the availability of the validated translations). Patients will be required to complete the questionnaires prior to any other assessments on Day 0 (CetuGEX™ patients only) and Day 1 of Cycle 1 (cetuximab patients only), respectively, as well as on Day 1 of Cycles 3 and 5 (i.e., 6 weeks and 12 weeks after randomization), 18 weeks after randomization and 28 (+ 2) days after last treatment administration (Safety Visit).

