In addition, for the QLQ-C30 scales, the difference with respect to baseline will be classified as  $\leq -10$ ,  $-10 - 10$ ,  $\geq 10$ . The rates of patients within these ranges will be presented by treatment group and visit. The time from randomization to the first occurrence of a deterioration of at least 10 points ( $\leq -10$  for global and functional scales,  $\geq 10$  for symptom scales) will be analyzed by Kaplan-Meier methods. Patients without occurrence of deterioration will be censored at the last assessment. The estimate of the quartiles of the time to deterioration as well as the associated 95%-confidence intervals will be tabulated by treatment arm together with the p-value of a log rank test.

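### The baseline quality-of-life forms are completed after randomization, when patients can already know their arm, so the change-from-baseline analyses use a reference value that allocation can influence

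*Protocol*

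**What the plan says.** Protocol 9.6 states that "Blinding at the level of study treatment does not apply since the study will be open label". Under Protocol 10.1.2, "the investigator will contact the IWRS for randomization information within 1 to 3 days prior to the next scheduled visit", and for the patient: "The patients do not need to visit the study site for this procedure but can be informed by phone". Protocol 9.5 and the Schedule of Events (18.1) give matching timing.

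The Screening Visit list (10.1.1) and the screening column of 18.1 contain no QoL questionnaire. Under Protocol 10.3.2, CetuGEX patients "complete the questionnaires prior to any other assessments on Day 0", and cetuximab patients do so on Day 1 of Cycle 1. Protocol 10.1.3 adds: "The Day 0 visit is not applicable for patients randomized to receive cetuximab". Protocol 9.3 requires CetuGEX patients to take paracetamol 1 g the evening before the infusion. For cetuximab it requires an antihistamine and a corticosteroid before the first infusion, with no evening paracetamol.

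SAP 7.1 takes the last value before administration as baseline, which for QoL is the Day 0 or Day 1 form. SAP 11.6 uses it for changes in all QLQ-C30 and H&N35 scores, with Wilcoxon p-values. For QLQ-C30 only, it also uses it for classes cut at 10 points and for "The time from randomization to the first occurrence of a deterioration of at least 10 points", with a log-rank test.

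**The concern.** A baseline is useful in a between-arm comparison because allocation cannot have affected it. Here it can, by two routes.

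The first is knowledge of the arm. A patient may have been told by phone. Even without a call, attending a Day 0 visit shows the arm, because only one arm has that visit. Completing the form before dosing and before the other assessments protects against effects of the drug and of the visit, but not against that knowledge.

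The second is the evening paracetamol, given in one arm only and before that arm's baseline form. SAP 11.6 scores pain in both questionnaires and use of pain killers in H&N35 (item 31).

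If baseline scores shift differently by arm, the shift passes into every comparison of change and can move patients across the 10-point threshold. Neither document plans a pre-randomization form, an adjustment or a sensitivity analysis. Adjusting for the recorded baseline would not help, since that value may itself be affected.

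**Working it through.** **Sequence, from the documents**

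| Step | CetuGEX | Cetuximab | Source |
|---|---|---|---|
| Screening, within 28 days before first infusion | no QoL form | no QoL form | Protocol 10.1.1, 18.1 |
| Allocation obtained, patient can be told | 1 to 3 days before the visit | 1 to 3 days before the visit | 10.1.2 |
| Evening before first infusion | paracetamol 1 g | none required | 9.3 |
| First QoL form | Day 0, pre-dose | Day 1, pre-dose | 10.1.3, 10.3.2 |

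In both arms the form follows randomization. Protocol 10.1.3 also says that CetuGEX patients receive their randomization number at the Day 0 visit. This fits poorly with notification by phone in 10.1.2, and the two should be reconciled. On either reading the visit is arm-specific and comes after allocation.

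**The plan's own figure.** The only sizing is for PFS, and it is not in dispute. Schoenfeld events = 4 × (1.960 + 0.842)² / [ln(5.6/8.4)]² = 31.40 / 0.1644 = 191, against 192 stated. There is no sample size, SD or power for QoL.

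**Illustration of size.** The following are assumptions, not in the documents: normal change scores, SD 20 or 25, 80 to 120 evaluable patients per arm, no true effect, and a shift of d points that affects one arm's baseline only and is gone by the next form. For a functional scale:

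- Deterioration at one visit = Φ((−10 − d)/SD) if that arm's baseline is d lower, or Φ((−10 + d)/SD) if it is d higher.
- With no shift: Φ(−0.5) = 0.309 for SD 20; Φ(−0.4) = 0.345 for SD 25.
- The between-arm difference in mean change is biased by d, with SE = SD × √(2/n). The false-positive rate of a nominal 5% two-sided test is Φ(d/SE − 1.96) + Φ(−d/SE − 1.96), a normal approximation to the planned Wilcoxon test.

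| d | Deterioration, SD 20 (lower / higher baseline) | Deterioration, SD 25 (lower / higher baseline) | False-positive rate |
|---|---|---|---|
| 2 | 0.274 / 0.345 | 0.316 / 0.374 | 0.080 to 0.121 |
| 3 | 0.258 / 0.363 | 0.302 / 0.390 | 0.118 to 0.213 |
| 5 | 0.227 / 0.401 | 0.274 / 0.421 | 0.244 to 0.491 |

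In the last column the lower end is SD 25 with 80 per arm and the upper end is SD 20 with 120 per arm. For d = 5, SD 20, n = 120: SE = 20 × √(2/120) = 2.58, d/SE = 1.94, rate 0.491. The table covers a single visit; the planned endpoint is time to first deterioration over several forms.

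**The case against.** The strongest reply is that patients know their arm at every later form too. If knowledge of the arm shifts answers by a constant amount throughout, the shift cancels in the present change score and would not cancel with a pre-randomization baseline. Under the same SD of 20, a persistent 5-point negative shift in one arm gives 31% deteriorated in both arms now, but Φ(−0.25) = 40% against 31% with a screening baseline; for 2 points it is 34% against 31%. This stands as a limit. The change protects the reference value, not later reporting, and which baseline carries less bias in a given comparison depends on how long any shift lasts. The documents do not say.

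The present timing also has a rationale: it is pre-dose, first in the visit and closest to treatment start. Control is the approved standard of care and both arms receive the same chemotherapy, so strong disappointment is less plausible than against no treatment. A screening form may be up to four weeks old in a disease with an expected control median PFS of 5.6 months, so some decline before treatment would count as deterioration. That decline occurs before allocation can act, so it adds noise to both arms alike.

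A reader might infer that all QoL results are compromised and that no analysis could recover them. The documents do not support this. SAP Tables 14.5.6.1, 14.5.6.4, 14.5.6.7 and 14.5.7.1 give absolute scores; comparing post-baseline scores between randomized arms does not use the baseline form, and an absolute summary at baseline would show an arm difference there. The 10-point analyses do not extend to H&N35.

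**Conclusion.** The point holds as a limited weakness in a secondary endpoint. That the baseline follows randomization in an open-label trial, on arm-specific days and after an arm-specific analgesic dose, comes directly from the documents. It affects the change-from-baseline Wilcoxon tests for both questionnaires and, for QLQ-C30 only, the 10-point classes and time to deterioration.

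A reader might also infer that a bias of known size favors one arm. Nothing in the documents establishes this. The SDs and the 2- to 5-point shifts above are assumptions, and direction is open: if the evening dose had any effect, it could lower reported pain while raising reported use of pain killers. The claim is only that allocation can influence the reference value, and that this part is preventable. Primary PFS and the trial's sizing are unaffected.

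**What to change.** In Protocol 10.1.1, 10.1.2, 10.3.2 and 18.1, have both questionnaires completed at the Screening Visit, or otherwise after consent and before the IWRS randomization call. In SAP 11.6, define that form as the QoL baseline, as a stated exception to the last-pre-administration rule in SAP 7.1. Keep the Day 0/Day 1 form as a sensitivity baseline: agreement between the two would be reassuring, and disagreement would show how far the choice matters. Reconcile 10.1.2 and 10.1.3 on when the patient learns of the randomization. No change to premedication is proposed.

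For patients already randomized without a screening form, the SAP should tabulate the Day 0/Day 1 scores by arm and state that this baseline was post-randomization and unblinded.

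The cost is one more completion of the two questionnaires at an existing visit, with no extra visit and no extra patients. The baseline may be up to 28 days before first infusion, which adds non-differential noise. Open-label influence on later answers remains.

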10.1.3 Combination Treatment Phase

During the combination treatment phase, the patients will receive the study medication (CetuGEX™ or cetuximab) in combination with chemotherapy (cisplatin and 5-FU) for a maximum of 6 cycles of combined treatment. In case of toxicity of cisplatin, carboplatin may substitute cisplatin, but after completion of the first cycle at the earliest.

During the combination treatment phase, even if the chemotherapy is delayed for any reason (e.g., see Sections 9.9.3 and 9.9.4), the IMP (CetuGEX™ or cetuximab) administration may not be withheld and needs to be continued with weekly infusions as scheduled. Additionally, all assessments related to the weekly administration of CetuGEX™/cetuximab should be performed as scheduled (see *). Only assessments relevant for the determination of whether the patient is eligible to continue the chemotherapy treatment (i.e., vital signs measurements and safety laboratory tests) have to be repeated in relation to the next administration of chemotherapy (see also Schedule of Events, Section 18.1).

If the administration of CetuGEX™ or cetuximab is skipped for any reason (see Sections 9.9.1 and 9.9.2), e.g., on Day 8, all assessments scheduled for this study visit

day are to be performed as planned (i.e., including collection of blood samples for the determination of ADA and pre-dose samples for PK).

Table 10-1 displays the ideal treatment schedule for the combination treatment phase.

Table 10-1: Ideal treatment schedule – combination treatment phase

Treatment cycle	Week	Chemotherapy ^a	IMP ^{b,c}	
1	Week 1	D1 ^d D2 – D4	D1	
	Week 2		D8	
	Week 3		D15	
2	Week 4	D1 ^d D2 – D4	D1	
	Week 5		D8	
	Week 6		D15	
3	Week 7	D1 ^d D2 – D4	D1	
	Week 8		D8	
	Week 9		D15	
4	Week 10	D1 ^d D2 – D4	D1	
	Week 11		D8	
	Week 12		D15	
5	Week 13	D1 ^d D2 – D4	D1	
	Week 14		D8	
	Week 15		D15	
6	Week 16	D1 ^d D2 – D4	D1	
	Week 17		D8	Start of maintenance phase
	Week 18		D15	

a) If the chemotherapy is delayed, the IMP (CetuGEX™ or cetuximab) administration needs to be continued with weekly infusions as scheduled.

b) Starting with the second IMP infusion (Day 8 of Cycle 1), a time window of ± 1 day will be allowed for the weekly infusions (calculated from the previous infusion).

c) If the administration of CetuGEX™ or cetuximab is skipped for any reason (see Sections 9.9.1 and 9.9.2), e.g., on Day 8, all assessments scheduled for this study visit day are to be performed as planned (i.e., including collection of blood samples for the determination of ADA and PK).

d) The platinum-based chemotherapy should be given within 24 hours after the infusion of CetuGEX™/cetuximab. Administration of 5-FU should be started within 24 hours after the infusion of CetuGEX™/cetuximab.

D = day, W = week

Day 0, Cycle 1 (Week 1)

On Day 0 of Cycle 1, eligible patients randomized to receive CetuGEX™ will visit the study site to receive their unique randomization number and perform baseline assessments as listed below and to receive a priming dose of 60 mg on this visit, after all baseline/safety assessments have been performed. The Day 0 visit is not applicable for patients randomized to receive cetuximab. General baseline assessments scheduled for Day 0 will be performed on Day 1 for those patients randomized to cetuximab.

The following assessments will be performed on Day 0 for patients in the CetuGEX™ treatment arm:

- Confirmation of inclusion/exclusion criteria.
- Physical examination.
- Vital signs (blood pressure, heart rate and body temperature), body weight and BMI.
- 12-lead ECG, if not done within 7 days prior start of study medication administration during screening phase.
- Record ECOG performance status.
- Blood and urine sampling for safety laboratory (hematology, coagulation panel, blood chemistry and urinalysis).
- Pregnancy test for female patients of childbearing potential.
- Quality of life questionnaires EORTC-QLQ-C30 and EORTC-QLQ-H&N35 (to be performed prior to any other assessments).
- Recording of concomitant medication.
- Assessment of AEs.
- Blood sampling for ADA testing.
- Blood sampling for PK assessments prior to the start of infusion and after the end of infusion.
- Blood sampling for assessment of cytokines and other relevant blood proteins (to be performed pre-dose, one hour after start of infusion and at the end of infusion).
- Blood sampling for assessment of immune status (to be performed pre-dose).
- Infusion of 60 mg CetuGEX™ priming dose.

Day 1, Cycle 1 (Week 1)

Day 1 of Cycle 1 will be the first treatment day for patients randomized to receive cetuximab. For those patients randomized to receive CetuGEX™ Day 1 of Cycle 1 should be performed within 24 hours after Day 0.

Day 1 (of each treatment cycle)

On Day 1 of each treatment cycle, the following assessments will be performed:

- Confirmation of inclusion/exclusion criteria (to be performed only for patients receiving cetuximab).
- Physical examination.
- Vital signs (blood pressure, heart rate and body temperature), body weight and BMI.
- Record ECOG performance status (to be performed in Cycle 1 only for patients receiving cetuximab and for all patients in every following cycle).
- 12-lead ECG (to be performed pre-dose, in Cycles 3 and 5 only; in Cycle 1 to be performed only for patients receiving cetuximab and only if not done within 7 days prior start of study medication administration during screening phase; to be performed).
- Evaluation of tumor size by CT or MRI (to be performed pre-dose, in Cycles 3 and 5 only; same equipment and type of imaging as used at Screening is required throughout the study). Assessment of the head, neck, and chest; assessments of the abdomen will only be performed if at baseline metastases were confirmed or if clinical evidence suggests new lesions in these regions.
- Blood and urine sampling for safety laboratory (hematology, coagulation panel, blood chemistry and urinalysis) (to be performed pre-dose, in Cycle 2 and every following cycle; in Cycle 1 to be performed only for patients receiving cetuximab).
- Pregnancy test for female patients of childbearing potential (in Cycle 1 only; to be performed only in patients receiving cetuximab).
- Blood sampling for assessment of cytokines and other relevant blood proteins* (to be performed only in a subset of approximately 30 patients per treatment arm; in Cycles 1 and 2 only: Cycle 1: pre-dose, at the start of the highest IMP infusion rate, 1 hour after start of the highest infusion rate and at the end of infusion; Cycle 2: pre-dose, 1 hour after start of infusion and at the end of infusion).
- Blood sampling for assessment of immune status* (to be performed only in a subset of approximately 30 patients per treatment arm; pre-dose on Day 1 of Cycle 1 for patients receiving cetuximab).
- Blood sampling for ADA testing* (to be performed only for patients receiving CetuGEX™; pre-dose on Day 1 of Cycle 2 and Cycle 4 only).
- Blood sampling for PK assessments* (only for patients receiving CetuGEX™; to be performed prior to start of infusion and at the end of infusion in Cycles 1 to 4 only).
- Blood sampling for additional PK assessments* (only for a subgroup of approximately 30 patients receiving CetuGEX™; to be performed 5 (\pm 5 min) and 7 (\pm 15 min) hours after start of infusion on Cycles 1 and 4 only).

- QoL questionnaires EORTC-QLQ-C30 and EORTC-QLQ-H&N35* (to be performed prior to any other assessments; to be performed in Cycles 3 and 5 only; in Cycle 1 to be performed only for patients receiving cetuximab).
- Study drug administration (CetuGEX™ according to infusion scheme as provided in Section 9.3 or cetuximab according to standard of care). Except for Day 1 of Cycle 1 a time window of ± 1 day will be allowed for the weekly infusions (calculated from the previous infusion).
- Administration of cisplatin (or carboplatin) and 5-FU (to be started not sooner than 1 hour after end of CetuGEX™/cetuximab infusion). The platinum-based chemotherapy should be given within 24 hours after the infusion of CetuGEX™/cetuximab. Administration of 5-FU should be started within 24 hours after the infusion of CetuGEX™/cetuximab. Cisplatin is mandatory in Cycle 1 and can be replaced with carboplatin in case of unacceptable toxicity in the subsequent cycles.
- Drug accountability.
- Recording of concomitant medication.
- Assessment of AEs.

Days 2 to 4 (of each treatment cycle)

Visits on Days 2 to 4 are only obligatory for patients who may not have a transportable pump for 5-FU administration on Days 2 to 4 and/or who are included in the subgroup of 30 CetuGEX™ patients for additional PK assessments.

On Day 2, Day 3 and Day 4 of each treatment cycle, the following assessments will be performed for patients visiting the site:

- Vital signs (blood pressure, heart rate and body temperature).
- Blood sampling for PK assessments*, for a subgroup of 30 CetuGEX™ patients only, and only during Cycles 1 and 4:
 - 24 ± 1 hours after start of infusion (Day 2)
 - 48 ± 2 hours after start of infusion (Day 3)
 - 72 ± 2 hours after start of infusion (Day 4).
- Administration of 5-FU (if not automatically performed by transportable pump).
- Drug accountability.
- Recording of concomitant medication.
- Assessment of AEs.

Days 8 and 15 (of each treatment cycle)

On Day 8 and Day 15 of each cycle of the combination treatment phase, the following assessments will be performed:

- Physical examination.
- Vital signs (blood pressure, heart rate and body temperature), body weight and BMI.
- Record ECOG performance status.
- Blood sampling for assessment of cytokines and other relevant blood proteins*, (to be performed only in a subset of approximately 30 patients per treatment arm; pre-dose, 1 hour after start of infusion and at the end of infusion in Cycle 1 only).
- Blood sampling for assessment of immune status* (to be performed only in a subset of approximately 30 patients per treatment arm; pre-dose on Day 8 of Cycle 2 only).
- Blood sampling for ADA testing* (to be performed only for patients receiving CetuGEX™; pre-dose on Day 8 of Cycle 1 only).
- Blood sampling for PK assessments* (only for patients receiving CetuGEX™; to be performed prior to start of infusion and at the end of infusion, in Cycles 1 to 3 only).
- Blood sampling for additional PK assessments* (only for a subgroup of approximately 30 patients receiving CetuGEX™; to be performed prior to start of infusion, on Day 8 of Cycle 4 only).
- Administration of CetuGEX™/cetuximab.
- Drug accountability.
- Recording of concomitant medication.
- Assessment of AEs.

It will be accepted that assessments of Days 8 and 15 will be performed one day before the infusion.

